f Urine pregnancy tests will be performed for any woman of childbearing potential (defined as all women who were not surgically sterile or postmenopausal for at least 1 year prior to informed consent). Pregnancy is not exclusionary for enrolment and pregnancy during the study does not lead to discontinuation.

g Only adverse events related to study procedures and/or study conduct should be collected in the eCRF.

h Concomitant medications are all medications taken during the study, including any prescribed medication-assisted treatment (methadone, naltrexone, buprenorphine) and will be captured. Of note, any extended-release buprenorphine treatment initiation will lead to study discontinuation.

i Ask about the subject's illicit buprenorphine use in the last 14 days. If the subject has used prescribed and not illicit buprenorphine, capture in Concomitant Medications. Illicit use will not impact the subject's participation on the study.

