#### 13.1 DESCRIPTIVE ANALYSIS

The number and percentage of subjects with negative and positive results for buprenorphine on the qualitative UDS will be summarized for FAS Part A at Visit 1 and for FAS Part B across Visits 1, 2 and 3. Qualitative UDS results for opioids other than buprenorphine will be summarized in a similar way.

The number and percentage of subjects with negative results for **both** buprenorphine and norbuprenorphine based on quantitative UDS or free drug concentrations will be summarized for FAS Part A at Visit 1 and for FAS Part B across Visits 1, 2 and 3. Negative and positive results for each analyte will also be summarized (buprenorphine, norbuprenorphine and naloxone for quantitative UDS; buprenorphine and norbuprenorphine for free drug concentrations). A negative result will be any concentration below the lower limit of quantification (LLOQ). A positive result will be any quantifiable concentration.

As for urine, the number and percentage of subjects with negative results for **both** buprenorphine and norbuprenorphine concentrations in plasma will be summarized for FAS Part A at Visit 1 and for FAS Part B across Visits 1, 2 and 3. Negative and positive results for each analyte (buprenorphine, norbuprenorphine) will also be summarized. A negative result will be any concentration below the LLOQ. A positive result will be any quantifiable concentration.

For all above tables, missing data will not be imputed. For Visits 2 and 3, data associated with the reported use of illicit buprenorphine at the visit or the use of prescribed buprenorphine within 3 weeks of the assessment will be excluded from all the above summary statistics calculation for that visit only. Those excluded data, if any, will be indicated in the listings. With respect to Visit 1, no data should be excluded since meeting the exclusion criteria infers that there was no use of prescribed or illicit opioid use within 3 weeks prior to the Screening visit.

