For the following descriptive analyses, the PK analysis set will be used. A graphical representation of buprenorphine and norbuprenorphine plasma/urine concentrations over time will be provided. Individual plasma/urine concentration-time data will be plotted using the time elapsed from the last SUBLOCADE dose. A solid line will be used to link concentrations from a same subject. Concentrations of buprenorphine and norbuprenorphine in urine (from quantitative UDS or free drug concentration assessments) will be presented with and without correction by creatinine concentration in urine (Appendix 4). The purpose of the correction by creatinine urine concentration is to correct for urinary dilution.

For plasma and urine (uncorrected) concentration-time plots, concentrations below the LLOQ will be imputed with the LLOQ value. Three symbols will be used for 1) quantifiable concentrations, 2) concentrations below the LLOQ and 3) quantifiable concentrations associated with the reported use of illicit buprenorphine at the visit or the use of prescribed buprenorphine within 3 weeks of the visit. For concentration-time plots representing buprenorphine or norbuprenorphine urine concentrations after correction with creatinine concentration in urine, concentrations below the LLOQ will not be imputed and will not be shown on the plots.

Norbuprenorphine-to-buprenorphine ratios will be calculated from quantifiable concentrations in plasma, quantifiable concentrations of free drug in urine, and quantifiable concentrations from quantitative UDS. Values will be reported in listings. Summary statistics (mean, SD, median, 5th and 95th percentiles, minimum, maximum) will be calculated by subgroups defined by the intake (yes/no) of prescribed or illicit buprenorphine. One subject may contribute to multiple observations (up to 3).

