### 13.2.2 Dataset Preparation

Buprenorphine plasma concentration data collected in Parts A and B will be merged with the previous NONMEM dataset that was used to develop the population model presented in Section 13.2.1.

R software version 3.4.3 or older will be used for data inspection and for the preparation of the input datafile for the population PK analysis in NONMEM. This will involve obtaining the required study variables from the primary data source for the current and previous studies, calculating the elapsed time from the last SUBLOCADE dose in Study RB-US-13-0003 or Study INDV-6000-301, and merging with the previous dataset combining Phase II/III data. All R codes related to data preparation, identification of potential outliers, and exploratory graphical analysis will be adequately commented for ease of use.

The NONMEM input file will be formatted as a comma separated (.csv) file and will include the following information: subject unique identification number, dosing information, actual sampling times, measured buprenorphine plasma concentrations, demographics (e.g., sex, age, weight, body mass index [BMI], race), study identification number, and flags for potential outliers and concentrations below the LLOQ.

Plasma concentrations below the LLOQ in the current study will be included in the analysis and will be handled using appropriate likelihood-based methodology.

Plasma concentrations associated with the reported use of illicit buprenorphine at the visit or the use of prescribed buprenorphine within 3 weeks of the visit (Part B – Visits 2 and 3) will be flagged as outliers, and although listed in the NONMEM dataset, will not be used for the population PK analysis.

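### The Visit 2-3 negative/positive tables drop below-LLOQ results from subjects who report buprenorphine use, although those results are valid depot negatives; a bounded table beside the planned one would keep them

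*SAP*

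**What the plan says.** SAP 13.1 summarises negative and positive results at Visit 1 for FAS Part A and across Visits 1 to 3 for FAS Part B. The tables cover the qualitative UDS, the quantitative UDS, free drug in urine, and plasma. For the concentration tables, negative means below LLOQ.

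At Visits 2 and 3, the plan removes "data associated with the reported use of illicit buprenorphine at the visit or the use of prescribed buprenorphine within 3 weeks of the assessment" from all of these tables, for the affected visit alone. The rule does not look at the result. The data are not discarded: "Those excluded data, if any, will be indicated in the listings". Nothing is excluded at Visit 1.

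The plots in SAP 13.1 work differently. On the uncorrected concentration-time plots, which include the primary-endpoint plasma plot (Protocol section 3), the use symbol is reserved for "quantifiable concentrations associated with the reported use of illicit buprenorphine at the visit", and likewise after prescribed use within 3 weeks. A user's below-LLOQ value is plotted at the LLOQ with the same symbol as any other below-LLOQ value.

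In SAP 13.2.2, Visit 2-3 plasma samples with reported use "will be flagged as outliers, and although listed in the NONMEM dataset, will not be used for the population PK analysis". Other below-LLOQ samples from this study enter through a likelihood method.

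Illicit use is captured at Visits 2 and 3 by a question on "illicit buprenorphine use in the last 14 days" (Protocol Appendix 1). Under Protocol 5.5.1, subjects who start transmucosal buprenorphine stay in the study.

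**The concern.** The exclusion is meant to stop new buprenorphine from being mistaken for depot buprenorphine. That risk exists only when the result is quantifiable. A below-LLOQ result after reported use cannot be contaminated in that sense: the depot contribution is no larger than the total, and the total is below LLOQ. Such a result answers the study's question, yet it leaves the tables together with the doubtful positives.

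Excluding all users amounts to assuming that users and non-users have the same share of depot negatives. If subjects use because their level has run out, the planned percent positive is too high. If users are more often still depot-positive, it is too low. Part B has at most 30 subjects, so a handful of excluded visits moves the percentage visibly.

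**Working it through.** **Inputs.** From the documents: at most 30 subjects in Part B (Protocol 5.1), and the exclusion rule and definition of negative in SAP 13.1. Not in the documents, and therefore assumed: the number of users, the share of depot negatives among users and non-users, and the LLOQ value. The plan states no figure on this point to reproduce.

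**Step 1, notation at one visit for one analyte.** *n* subjects with a result; *u* report use; *x* negatives among the *n − u* non-users; *m* negatives among the users.

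- Planned percent negative = *x*/(*n − u*).
- A user negative is certainly depot-negative; a user positive is undetermined. The depot-negative share therefore lies between (*x + m*)/*n* and (*x + u*)/*n*.
- The planned percent positive is above anything the data allow only if *m/u* > *x*/(*n − u*).

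**Step 2, an example (assumed counts).** *n* = 30, *u* = 6, *x* = 8. Planned percent positive = 1 − 8/24 = 66.7%, whatever *m* is. The lower limit of the range is 1 − 14/30 = 53.3% throughout.

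| User negatives *m* | Possible depot-positive share |
|---|---|
| 0 | 53.3% to 73.3% |
| 2 | 53.3% to 66.7% |
| 3 | 53.3% to 63.3% |
| 4 | 53.3% to 60.0% |

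With 3 or more user negatives, the planned 66.7% lies outside what the data allow. With none, it lies inside, and the truth may be on either side of it.

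**Step 3, expected error of the planned table.** With depot-negative shares *pN* in non-users and *pU* in users, error in percent positive = *u*(*pU − pN*)/*n*. Take *pN* = 30%.

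| Users of 30 | *pU* = 50% | *pU* = 30% | *pU* = 10% |
|---|---|---|---|
| 3 | +2.0 points | 0 | −2.0 points |
| 6 | +4.0 points | 0 | −4.0 points |
| 9 | +6.0 points | 0 | −6.0 points |

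**Step 4, the same in terms of use rates.** Let half of Part B be truly negative.

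- Use 30% in negatives, 15% in positives: planned percent negative = 0.5 × 0.70/(0.5 × 0.70 + 0.5 × 0.85) = 45.2%, so percent positive is 4.8 points too high.
- Use 40% against 20%: 0.5 × 0.60/(0.5 × 0.60 + 0.5 × 0.80) = 42.9%, or 7.1 points too high.
- Swapping the rates gives 54.8% and 57.1%, so percent positive is 4.8 and 7.1 points too low.

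**Step 5, two alternatives that do not work.**

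- *Add back user negatives and still drop user positives.* Percent negative becomes (*x + m*)/(*n − u + m*), which selects on the result. With equal shares of 30% in users and non-users, 3 to 9 users, and a probability of 0.25 to 1 that the added drug is itself below LLOQ, percent positive is 0.6 to 8.0 points too low, where the planned rule has no error.
- *In the PK fit, left-censor a user's quantifiable sample at its measured value.* That limit equals depot plus added drug, so it depends on the quantity being estimated. In a simulation with assumed inputs (lognormal depot level, log-SD 0.7, LLOQ 0.05 ng/mL, 30% users, use unrelated to depot level), the true share above LLOQ was 50%. Exclusion recovered 50%; censoring gave 40% to 47% with median added drug of 0.01 to 0.1 ng/mL.

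**The case against.** The strongest defence is that the rule drops positives and negatives alike, so losing negatives does not by itself overstate persistence. That stands. A reader might infer that the plan inflates persistence, but this needs users to be more often depot-negative than non-users, and the documents say nothing on that association.

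Second, these tables do not carry the persistence estimate. Protocol 1.3 assigns the percentage of positive and negative urine samples to Part A. Part B admits only subjects with a positive quantitative UDS at Visit 1, so its percentages are already conditional, and they are not among the endpoints in Protocol section 3. In Step 4, 30 subjects leave about 21 to 23 in the table, with a binomial standard error of about 10 points (√(0.452 × 0.548/23) ≈ 0.10), larger than the shift. This stands and limits the severity.

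Third, a reader might infer that below-LLOQ results among users will be common. Simulating the Table 1 sublingual parameters, a single 8 mg film taken at a random time 0.5 to 14 days earlier contributes less than an assumed 0.05 ng/mL in 66% of cases. With 14 daily 8 mg doses the figure is 0% when the last dose was 2 to 24 hours earlier and 5% at 1 to 3 days. Both dosing patterns are assumptions, and the calculation covers only plasma buprenorphine, not norbuprenorphine or urine. No claim about frequency is supported.

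Fourth, a plot may show every observation while a table is restricted. That is fair: the two treatments differ without contradicting each other. It is also too strong to call the data deleted. They stay in the listings and the NONMEM file, and prescribed use more than 3 weeks earlier is not excluded at all.

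What survives is that certain negatives are set aside when they could narrow the answer at almost no cost.

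**Conclusion.** The concern holds as a minor point about the Visit 2-3 buprenorphine and norbuprenorphine tables. The exclusion ignores the result, and so drops below-LLOQ values that reported use cannot have produced. It is unbiased if use is unrelated to remaining depot drug. Otherwise percent positive can be off in either direction by about 2 to 7 points, under the assumed numbers of users and rates in Steps 3 and 4.

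The range in Step 1 needs no assumption about how use relates to depot status. It does need reported use to be complete, since an unreported user's positive would still count as depot drug. Visit 1 and the primary plasma plot are not affected.

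A reader might extend the argument to SAP 13.2.2 and ask for user samples to be put back into the model. Step 5 shows why that does not follow: when use is unrelated to depot level, exclusion is unbiased, whereas left-censoring the quantifiable samples pulls modelled persistence down. Adding back only the below-LLOQ samples does the same, because it selects on a low result.

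**What to change.** In SAP 13.1, keep the planned Visit 2-3 tables and add beside them, for buprenorphine and norbuprenorphine, a table of all subject-visits with a result:

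- below-LLOQ results (or negative qualitative screens) counted as negative whether or not use was reported;
- quantifiable or positive results without reported use counted as positive;
- quantifiable or positive results with reported use in a separate row, 'positive, source indeterminate';
- percent depot-negative as a range, from all indeterminate results taken as positive to all taken as negative.

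The naloxone and other-opioid summaries need no change, because the depot argument does not apply to them.

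In SAP 13.2.2, keep the exclusion of use-associated samples as the main fit. Do not left-censor users' quantifiable samples at their measured value, and do not add back only their below-LLOQ samples.

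The cost is a short SAP edit and one extra row, with no new data. The downside is a range beside a single percentage, and it will be wide if many users have quantifiable results.

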### **5.4 Part B Continuation Criterion**

Results on the quantitative UDS performed at Visit 1 will determine enrolment in Part B:

- Subjects who provide a quantifiable (i.e., positive) result for buprenorphine and/or norbuprenorphine and a non-quantifiable (i.e., negative) result for naloxone will continue into Part B of the study if Part B is still open to enrolment.
- Subjects who achieve negative results for both buprenorphine and norbuprenorphine quantitative UDS (irrespective of naloxone result) at Visit 1 will conclude their study participation, as will subjects who achieve a positive result for buprenorphine and/or norbuprenorphine and a positive result for naloxone on the quantitative UDS performed at Visit 1.

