#### 6.1.3 Full Analysis Set (FAS)

**FAS Part A:** The FAS Part A consists of all subjects who are screen success and who have at least one measure of buprenorphine or norbuprenorphine concentration in plasma or at least one measure of buprenorphine or norbuprenorphine concentration in urine (as free drug or from quantitative UDS) or at least one measure for buprenorphine qualitative UDS in Part A (from Scheduled or Unscheduled visits).

**FAS Part B:** The FAS Part B consists of all subjects who met continuation criteria for Part B and who have at least one measure of buprenorphine or norbuprenorphine concentration in plasma or at least one measure of buprenorphine or norbuprenorphine concentration in urine (as free drug or from quantitative UDS) or at least one measure for buprenorphine qualitative UDS in Part B (from Scheduled or Unscheduled visits).

The FAS consists of all subjects who are part of FAS Part A and/or FAS Part B.

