#### **6.1.4 Pharmacokinetic Analysis Set**

The PK Analysis Set consists of all subjects who are screen success and who have at least one concentration measure for buprenorphine or norbuprenorphine in plasma or urine.

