## 7. SUBJECT DISPOSITION

The number and percentage of subjects screened and considered as screen failures, if any, will be summarized. A listing of the inclusion/exclusion reasons for screen failures will be provided, if any.

The number and percentage of subjects in populations of Safety Analysis Set Part A, Safety Analysis Set Part B, FAS Part A and FAS Part B together with the number and percentage of subjects who completed Part A and the number of subjects who completed Part B will be summarized. The population in the Safety Analysis Set will be used as denominator to calculate the percentage. A completer for Part A is the subject in the Safety Analysis Set Part A who has completed all plasma and urine sample collections for Visit 1 (Scheduled or Unscheduled) for Part A. A completer for Part B is the subject in the Safety Analysis Set Part B who has completed all plasma and urine sample collections for Visits 2 and 3 (Scheduled or Unscheduled) in Part B. The reasons Part A subjects did not participate in Part B will be summarized.

If a subject completes Part B but does not complete Part A, a footnote will be added to clarify.

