## 8. PROTOCOL DEVIATIONS

A protocol deviation (PDV) is any change, divergence, or departure from the study design or procedures defined in the protocol as per ICH E3 guidelines. Important PDVs are a subset of protocol deviations that may significantly impact the completeness, accuracy, and/or reliability of the study data or that may significantly affect subject's rights, safety, or well-being.

A listing of PDVs, classified as important and not important, will be presented by subject using the Safety Analysis Sets. Except for important PDV defined as below, all other deviations are considered as non-important PDV:

- The subject was deemed eligible for the study but did not meet key inclusion criteria as listed below:
  - The subject participated in Study RB-US-13-0003 or both Studies RB-US-13-0003 and INDV-6000-301 and received at least 2 SC injections of SUBLOCADE.
  - The subject must be within 12 months to the last day of the 36th months post his or her last SUBLOCADE injection at the time of the Screening visit.
  - The subject did not provide the informed consent prior to the start of any study procedures.
- Subject was deemed eligible for the study but did not meet key exclusion criteria as listed below:
  - The subject received SUBLOCADE or any other long-acting buprenorphine product at any time after ending their participation in Study RB-US-13-0003 or Study INDV-6000-301.
  - The subject has taken any buprenorphine (prescribed or illicit) within 3 weeks prior to the Screening visit.
- Part B continuation criteria: The subject did not meet Part B continuation criterion but continued to Part B.

- The subject was not discontinued after reporting use of SUBLOCADE or any other long-acting buprenorphine product during the study as specified in protocol Section 5.5.

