Relationships between plasma and urine drug concentrations measured on the same day will also be explored by calculating urine-to-plasma ratios for quantifiable concentrations of buprenorphine or norbuprenorphine. Urine drug concentrations corrected by creatinine concentration or uncorrected will both be used to derive those urine-to-plasma concentration ratios. Values will be reported in listings. Summary statistics (mean, SD, median, 5th and 95th percentiles, minimum, maximum) will be calculated by subgroups defined by the intake (yes/no) of prescribed or illicit buprenorphine. One subject may contribute to multiple observations (up to 3).

Finally, plots will be constructed to assess the consistency of norbuprenorphine-to-buprenorphine ratios and of urine-to-plasma concentration ratios over time, using the time elapsed from the last SUBLOCADE dose. A solid line will be used to link data from a

same subject. Different symbols will be used by subgroups defined by the intake (yes/no) of prescribed or illicit buprenorphine.

Equations for correction of buprenorphine or norbuprenorphine urine concentrations or urine-to-plasma concentration ratios with creatinine concentration in urine are presented in Appendix 4.

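### Visit 1 data are kept on a presumption of no recent buprenorphine use, and naloxone results flag no sample in the analysis at any visit

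*SAP*

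**What the plan says.** **Visit 1 rule.** For the positive/negative summaries, SAP 13.1 states: "With respect to Visit 1, no data should be excluded since meeting the exclusion criteria infers that there was no use". The sentence goes on to speak of opioid use, whereas exclusion criterion 2 (Protocol 5.3) concerns buprenorphine only. For Visits 2 and 3, the same section removes data linked to reported illicit buprenorphine at the visit or prescribed buprenorphine in the preceding 3 weeks.

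**Possible breach.** Among the important deviations in subjects deemed eligible, SAP 8 lists: "The subject has taken any buprenorphine (prescribed or illicit) within 3 weeks prior to the Screening visit". No data-handling rule is attached.

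**Naloxone.** The quantitative urine screen includes naloxone at every visit. Protocol 5.4 ends participation after Visit 1 for subjects negative on both analytes, "as will subjects who achieve a positive result for buprenorphine and/or norbuprenorphine and a positive result for naloxone on the quantitative UDS". SAP 13.1 counts naloxone as one more analyte and does not cross it with the buprenorphine results.

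**Analysis sets.** SAP 6.1.3: "The FAS Part B consists of all subjects who met continuation criteria for Part B and who have at least one measure". FAS Part A needs only screen success and a measurement. SAP 6.1.4: "The PK Analysis Set consists of all subjects who are screen success and who have at least one concentration measure for buprenorphine or norbuprenorphine".

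**Plots, ratios, model.** The special plot symbol is for "quantifiable concentrations associated with the reported use of illicit buprenorphine at the visit or the use of prescribed buprenorphine within 3 weeks" of the visit. Ratio summaries "will be calculated by subgroups defined by the intake (yes/no) of prescribed or illicit buprenorphine". SAP 13.2.2 withholds use-associated concentrations from the population PK fit, but names only Part B Visits 2 and 3. SAP 13.2.3 allows outliers to be removed after visual inspection and on documented information.

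**The concern.** The Visit 1 rule treats eligibility as proof of no recent use, while SAP 8 allows that an enrolled subject may have breached that very criterion. Read literally, even a recorded breach stays in the Part A tables and the model dataset.

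Naloxone is a laboratory result that the study already holds, and it matters enough to stop a subject entering Part B. In the analysis, every rule that separates recent use rests on reported, prescribed or undefined intake.

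Visit 1 is the only visit in Part A. Protocol 1.3 expects Part A to inform long-term exposure and the percentage of positive urine samples. If some naloxone-positive samples came from another buprenorphine source, the results would attribute them to residual SUBLOCADE. Metabolite ratios could mix sources too: Protocol 1.2 gives norbuprenorphine/buprenorphine AUC ratios of 0.2–0.4 for SUBLOCADE and 1.3–3.2 for transmucosal buprenorphine.

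**Working it through.** The plan has no figure to reproduce here: the 60 subjects rest on practical considerations. The check is to follow the samples through the rules and then size the effect under assumed counts.

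**Step 1. Where the two kinds of sample go**

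| Analysis | Recorded breach or prescribed use at Visit 1 | Naloxone-positive, no reported use |
|---|---|---|
| Positive/negative tables (SAP 13.1) | Kept at Visit 1; comparable use removed at Visits 2–3 | Kept at any visit |
| Primary plasma plot (SAP 13.1) | Own symbol if quantifiable and covered by the reported/prescribed-use rule | Ordinary symbol |
| Ratio summaries (SAP 13.1) | Intake group, if intake is known | Probably the no-intake group; intake is not defined |
| Population PK (SAP 13.2.2, 13.2.3) | Not covered by the Visit 2–3 flag | May enter; removal is discretionary |

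I read screen success as including subjects deemed eligible in error. FAS Part B excludes subjects who were naloxone-positive at Visit 1, but nothing comparable applies to samples taken at Visits 2 and 3. The outlier definition in SAP 13.2.3 is deviation from the same individual's other observations, which suits a single sample in this study poorly.

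**Step 2. Urine positivity, quantitative screen, either analyte**

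N = 60 (Protocol 14.2, SAP 15). Assumed: x flagged subjects, y other positives. Kept = (x + y)/60; left out = y/(60 − x).

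| x | y | Kept | Left out | Shift (points) |
|---|---|---|---|---|
| 1 | 30 | 51.7% | 50.8% | 0.8 |
| 1 | 20 | 35.0% | 33.9% | 1.1 |
| 3 | 20 | 38.3% | 35.1% | 3.2 |
| 6 | 10 | 26.7% | 18.5% | 8.1 |

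For x from 1 to 6 and y from 10 to 30, these give the smallest and largest shifts. If the true rate of such samples were 1%, 2% or 5% (assumed), the chance of at least one in 60, 1 − (1 − rate)^60, is 45%, 70% or 95%.

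**Step 3. Plasma positivity**

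If every flagged subject is plasma-positive, Step 2 applies. If none is, kept = y/60 and left out = y/(60 − x), so leaving them out raises the percentage: x = 3, y = 20 gives 33.3% to 35.1%, and the range is 0.3 to 5.6 points. The direction is not fixed.

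**Step 4. Plasma metabolite ratio in the no-intake group**

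Assumed: depot ratios uniform on 0.2–0.4 (mean 0.30), flagged ratios uniform on 1.3–3.2 (mean 2.25). For n depot and x flagged observations, mean = (0.30n + 2.25x)/(n + x). The other columns are averages over 40,000 simulated data sets.

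| n | x | Mean | SD | Median | 95th percentile |
|---|---|---|---|---|---|
| 20 | 0 | 0.30 | 0.06 | 0.300 | 0.38 |
| 20 | 1 | 0.39 | 0.43 | 0.305 | 0.39 |
| 20 | 3 | 0.55 | 0.69 | 0.314 | 2.2 |
| 90 | 1 | 0.32 | 0.21 | 0.301 | 0.39 |
| 90 | 3 | 0.36 | 0.36 | 0.303 | 0.39 |

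If half the buprenorphine in a flagged sample is from the depot, its mean ratio is 0.5 × 2.25 + 0.5 × 0.30 = 1.275, and the n = 20 means become 0.35 (x = 1) and 0.43 (x = 3). Mean and SD can move materially; the median barely does.

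The effect on the population PK estimates was not quantified.

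**The case against.** **The premise is not documented.** No passage says what a naloxone result means or why it gates Part B. This stands. The inference rests on that gating role and on Protocol 1.1, whose description of SUBLOCADE lists no naloxone. It supports a sensitivity display, not removal from the main analysis. A reader might infer that Part A is known to contain samples from another source; the documents do not support that. A deviation category is not evidence that breaches occurred.

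**The effect on ratios and model is not certain.** A reader might infer that naloxone-positive samples necessarily enter the no-intake ratios and the fit. SAP 13.1 does not define intake, and SAP 13.2.3 could be used to drop such a concentration, since a naloxone result is documented information. Both are possible, neither is assured.

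**Much is visible already.** Criterion 2 is checked on the day of Visit 1, naloxone is tabulated, all data are listed, and SAP 7 says: "The reasons Part A subjects did not participate in Part B will be summarized". If those reasons follow Protocol 5.4, the count of joint positives and the adjusted urine percentage could be worked out by hand. No planned table, plot or fit shows the contrast, however.

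**Visit 1 has little use information.** The illicit-use question is scheduled only at Visits 2 and 3, and SAP 11 says prior medications are not collected. Extending the reported-use rule to Visit 1 can therefore draw mainly on recorded deviations and ongoing medications.

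**Size.** Every count is assumed. The sampling standard error at 35% of 60 is √(0.35 × 0.65/60), about 6 points. Bias and sampling error differ in kind, but this gives scale. The 8.1-point shift needs 10% of subjects flagged. The ratio ranges are AUC ratios from a repeat-dose study, not single samples 12 to 36 months later.

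**Conclusion.** The point holds in two parts. First, the Visit 1 rule and the limit of the population PK flag to Visits 2 and 3 conflict with the plan's own provision for a breach of criterion 2, and treat recorded use at Visit 1 differently from use at later visits. This needs no assumption about naloxone. Second, no analysis rule uses naloxone, so joint-positive samples without reported use remain ordinary data in the tables and primary plot at all three visits.

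The size is unknown and may be zero. Under the assumed counts, urine positivity shifts by 0.8 to 8.1 points, plasma positivity could move either way, and ratio means and SDs are more exposed than medians. These figures matter only if flagged samples exist and reflect another buprenorphine source. The study is descriptive and makes no formal tests, so this is an inexpensive improvement in pre-specification, not a defect that invalidates the results.

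**What to change.** - **Recorded use at Visit 1.** Replace the sentence in SAP 13.1 that keeps all Visit 1 data, and extend the SAP 13.2.2 flag. Visit 1 data with a recorded breach of criterion 2, or documented prescribed buprenorphine within 3 weeks (for example an ongoing concomitant medication), would then be handled as at Visits 2 and 3. Refer to buprenorphine rather than opioids.
- **Naloxone flag, all visits.** Flag any sample whose same-visit quantitative urine screen is quantifiable for naloxone together with buprenorphine and/or norbuprenorphine. Give it its own plot symbol and list its ratios separately.
- **Main and sensitivity analyses.** Keep naloxone-flagged samples in the main analysis. Report the Part A and Part B positive/negative tables and the population PK fit without them as a sensitivity analysis. State that the main fit feeds the SAP 13.2.6 simulations.

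The cost is SAP wording, a few extra tables and one extra model run, with no new data collected. The flag is partial: it misses buprenorphine products without naloxone, and naloxone may have another source. Because the flag requires a positive result, leaving flagged samples out can only lower quantitative-screen positivity on either analyte. That is why the version without them should stay secondary.
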